10.0 CRITERIA FOR REMOVAL FROM STUDY

Patients will be removed from study when any of the criteria listed in Section 7.3 applies. The reason for study removal and the date the patient was removed must be documented in the Case Report Form.

Noncompliance

Patient noncompliance of study medication will be defined as the patient voluntarily taking fewer than 80% of their assigned study medication. For example, out of 10 days of therapy the patient would need to miss at least 3 doses to be noncompliant. Temporary discontinuation of the investigational product by a physician's order due to adverse events or disease complication does not constitute non-compliance.

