3.0 PATIENT SELECTION

3.1 Eligibility Criteria

1. Patients with a cytologically confirmed diagnosis of breast cancer with a biopsy showing invasive or non-invasive breast cancer (DCIS) at least 1.0 cm greatest diameter on imaging (biopsy must have been performed within 6 months of screening visit).
2. Surgical patients, undergoing lumpectomy, subtotal or total mastectomy.
3. Age ≥ 18 years of age.
4. Female.
5. Patients must have tissue blocks available from diagnostic biopsy.
6. Negative pregnancy test, medical history of surgical sterilization, or 1 year post-menopausal. The effects of LEAG on the developing human fetus at the recommended therapeutic dose are unknown. For this reason women of child-bearing potential must agree to use adequate contraception (hormonal or barrier method of birth control; abstinence) prior to study entry and for the duration of study participation.
7. Patient must be willing to forgo surgery for a minimum of 5 days.
8. The ability and willingness to sign a written consent.
9. Patients currently being treated for hypertension must be on a stable dose of medication for the past 30 days.
10. Diabetic patients must be well controlled (HbA1c < 8.5 within past 60 days or documented fasting blood glucose < 140 mg/dl for three consecutive days). Known diabetics who have experienced episodes of symptomatic hypoglycemia in the last 6 months are also considered poorly controlled and will be excluded from study participation.
11. ECOG status of ≤ 2 or Karnofsky $\geq 60\%$ (Appendix F).

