3.2 Exclusion Criteria

1. Patients with previous or concurrent malignancy, excluding non-melanotic skin cancer. Malignancies treated and without recurrence or symptoms of recurrence within the last 3 years are acceptable.
2. Patients with evidence of distant metastatic disease.
3. Patients who have had chemotherapy, biologic or radiotherapy within 6 months of biopsy.
4. Patient usage of herbal supplements or alternative medications not approved by the FDA within 1 week of starting study drug. LEAG or related ginseng products, and combination products containing ginseng should be discontinued within 6 weeks of starting study drug.

5. Patients with a history of allergic reactions attributed to compounds of similar chemical or biologic composition to LEAG, including other products claiming to contain ginseng in any form.
6. Patients with a history of a chronic inflammatory process, including, but not limited to, rheumatoid arthritis and lupus. This includes patients on concurrent chronic systemic steroids or anti-inflammatory medications.
7. The subject has active bleeding (i.e. gastrointestinal ulcer with bleeding) or a pathological condition that carries a high risk of bleeding, in the investigator's opinion.
8. Patients with any swallowing dysfunction leading to difficulty taking the investigational therapy are ineligible for the study.
9. Uncontrolled intercurrent illness including, but not limited to, ongoing or active infection, symptomatic congestive heart failure, unstable angina pectoris, cardiac arrhythmia, or psychiatric illness/social situations that would limit compliance with study requirements. HIV-positive patients on combination antiretroviral therapy are ineligible because of the potential for pharmacokinetic interactions with LEAG. Appropriate studies will be undertaken in patients receiving combination antiretroviral therapy when indicated.
10. Patients with poorly controlled diabetes (control indicated with HbA1c \leq 8.5 within past 60 days or documented fasting blood glucose $<$ 140 mg/dl for three consecutive days). Known diabetics who have experienced episodes of symptomatic hypoglycemia in the last 6 months are also considered poorly controlled and will be excluded from study participation.

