11. Patients with uncontrolled hypertension (SBP $>$ 140 mmHg or DBP $>$ 90 mmHG). Should a subject's blood pressure on initial presentation fall above defined parameters for hypertension two additional blood pressure measurements will be performed at least 15 minutes apart. The initial blood pressure and two additional measurements will be averaged. If the average of the three measurements remains above the defined parameters for hypertension, the patient will be excluded. If the average of the three measurements falls below the defined parameters for hypertension, the patient will be considered to meet eligibility.
12. Pregnant or breast feeding women. Women must be willing to use birth control throughout study duration.
13. Patients on other investigational medications or having been treated with an investigational agent within 6 weeks prior to biopsy.
14. Patients currently receiving coumadin therapy or who have been treated with coumadin within the 2 weeks prior to biopsy.
15. Patients taking monoamine oxidase inhibitors.

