4.3 Criteria for Enrollment

- Confirmation that patient has met all of the Inclusion Criteria and none of the Exclusion Criteria.
- Patient has voluntarily signed informed consent document.

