7.3 Prohibited Concomitant Medications

7.3.1 Products Containing Ginseng

- All products containing or claiming to contain any form of ginseng product including oral and external application products are prohibited from use during this study and for six weeks prior to initial biopsy.

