7.3.2 Coumadin

- Due to a report concerning the possible interaction between coumadin and ginseng, patients currently being treated with coumadin are ineligible for the study.

All other medications, prescription, and over the counter, that affect platelets and/or clotting functions should be used with caution.

7.3.3 Herbal Supplements and Alternative Medications not approved by the FDA.

- All Herbal Supplements and Alternative Medications not approved by the FDA including oral and external application products are prohibited from use during this study and for six weeks prior to initial biopsy.

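### Exclusion 4 counts its supplement washout from first dose while Section 7.3 counts from the biopsy, so an eligible patient's baseline tissue can be exposed to ginseng or herbal products

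*Combined protocol and SAP*

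**What the plan says.** Two parts of the protocol set a washout for the same products.

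- **Exclusion 4 (Section 3.2)** rules out "Patient usage of herbal supplements or alternative medications not approved by the FDA within 1 week of starting study drug". For ginseng it says that LEAG, related products "and combination products containing ginseng should be discontinued within 6 weeks of starting study drug".
- **Section 7.3.1** covers everything sold as ginseng, and its ban reads: "form of ginseng product including oral and external application products are prohibited from use during this study and for six weeks prior to initial biopsy". **Section 7.3.3** sets the same window for unapproved herbal and alternative products, and its sentence ends: "the FDA including oral and external application products are prohibited from use during this study and for six weeks prior to initial biopsy".

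Entry depends on Section 3 alone. Section 4.3 asks for "Confirmation that patient has met all of the Inclusion Criteria and none of the Exclusion Criteria" and does not mention 7.3. On the age of the biopsy, inclusion 1 requires only that the "biopsy must have been performed within 6 months of screening visit".

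Section 10 then states: "Patients will be removed from study when any of the criteria listed in Section 7.3 applies". Section 6.6 holds a separate list of reasons to stop treatment: intercurrent illness, toxicity, withdrawal and change in condition.

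Under Section 16.0 each patient is her own control, and biopsy tissue is compared with surgical tissue by paired t-test or Wilcoxon signed-rank test.

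**The concern.** The trial has one arm and no untreated comparison, so the diagnostic biopsy is the only reference for ER, PR, Ki67, cyclin D1 and COX-2. Section 7.3 protects that reference by keeping the six weeks before it free of supplements. Exclusion 4 protects the run-up to first dose instead, and exclusion 4 decides who enters.

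The two product classes would distort the paired change differently.

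- **Herbal product at biopsy.** The change to surgery mixes starting LEAG with stopping the other product. The direction is unknown.
- **Ginseng at biopsy.** Both specimens are ginseng-exposed. If ginseng affects the markers, the measured change is pulled toward zero.

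Other prior-treatment washouts in Section 3.2 are counted from the biopsy: exclusion 3 (chemotherapy, biologic therapy, radiotherapy), exclusion 14 (coumadin), and exclusion 13, which covers patients "having been treated with an investigational agent within 6 weeks prior to biopsy". Exclusion 4 is the prior-treatment washout that leaves the baseline tissue open.

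The serum comparison is largely unaffected, because its baseline is drawn at Study Visit 1, shortly before LEAG starts.

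**Working it through.** The plan states no figure on this point, so the check is date arithmetic.

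**Inputs**
- Exclusion 4: herbal 7 days, ginseng 42 days, both before first dose. I read the ginseng clause as off ginseng for at least six weeks before first dose; a looser reading would widen the gap.
- Sections 7.3.1 and 7.3.3: 42 days before biopsy, both classes.
- G = days from biopsy to first dose. The documents give no value. I take 7 to 183 days as an assumed range, the upper end reflecting the 6-month allowance.
- L = days from last use of the product to first dose.

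**Conditions**
- Eligible under exclusion 4: L ≥ 7 (herbal) or L ≥ 42 (ginseng).
- Compliant with 7.3: L ≥ 42 + G (both).
- Range of L that is eligible but in breach: herbal (42 + G) − 7 = 35 + G days; ginseng (42 + G) − 42 = G days.
- Latest permitted stop relative to biopsy: herbal 7 − G, ginseng 42 − G (positive = days before biopsy, negative = days after).

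| G (days) | Herbal: eligible but in breach | Herbal: latest stop | Ginseng: eligible but in breach | Ginseng: latest stop |
|---|---|---|---|---|
| 7 | 42 | 0 | 7 | +35 |
| 14 | 49 | −7 | 14 | +28 |
| 42 | 77 | −35 | 42 | 0 |
| 183 | 218 | −176 | 183 | −141 |

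**Results**
1. For any G above 0, an eligible patient can breach 7.3 in either class.
2. Exposure at the biopsy itself is possible once G exceeds 7 days (herbal) or 42 days (ginseng).
3. For herbal products exclusion 4 is both shorter and later anchored. For ginseng both windows are 42 days and only the anchor differs.
4. An eligible herbal user has been off the product at surgery for at least 7 + 5 = 12 days on a 5-day course, or 7 + 14 = 21 days on a 14-day course. Section 2.6 hypothesizes that marker changes are detectable after 5 or more days of treatment. Applying that to withdrawal of another product is my extrapolation, but it shows that the interval is not negligible on the plan's own time scale.
5. Each affected patient is 1/25 = 4% or 1/50 = 2% of the sample. This is a weight, not a bias.

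**After re-anchoring.** If exclusion 4 required L ≥ 42 + G for both classes, the eligible-but-in-breach range would be 0 days at every G.

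**The case against.** The strongest objection is to reading Section 10 literally. A reader might infer that the plan enrolls these patients and then removes them on entry. The documents do not support resting the point on that. Section 7.3 is a list of prohibited medications, not of removal criteria: 7.3.2 speaks of ineligibility, and 7.3.4 concerns only the first five patients. The stopping criteria are in 6.6, and Section 10 probably meant to cite them. If so, removal on entry falls away. Removal and an exposed baseline in the analysis are in any case alternatives: a removed patient contributes no baseline, and a retained patient is not removed. Section 10 also requires the reason and date of any removal to be documented, so a late removal would be visible. This objection stands. It leaves the conflict between exclusion 4 and 7.3 untouched.

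Other objections stand in part.

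- **Not every criterion is anchored to the biopsy.** Exclusions 1 and 10 and inclusion 9 use other clocks. The comparison is only with the prior-treatment washouts 3, 13 and 14.
- **Records.** Sections 5.1.1 and 5.1.2 record history and concomitant medications at screening, so pre-biopsy use may be captured. What is missing is a specified last-use date reaching back to before the biopsy.
- **Long gaps may be rare.** The synopsis describes a new diagnosis, and imaging must fall within 6 weeks of treatment. Section 13.1 also limits baseline evaluations to 6 weeks before surgery, but it concerns lesion measurement, and the biopsy has its own 6-month window. Even if the limit applied, G could reach 42 − 5 = 37 days. Ginseng use at the biopsy would then be ruled out, but use up to 42 − 37 = 5 days before it would not, and herbal use at biopsy would remain possible.

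**Conclusion.** The point holds as a conflict between exclusion 4 and Sections 7.3.1 and 7.3.3, and nothing else in the protocol reconciles them. An eligible patient can breach 7.3. Her baseline tissue can be exposed when the biopsy precedes first dose by more than 7 days (herbal) or more than 42 days (ginseng). This affects the primary tissue comparison, where the biopsy is her only control.

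The size is limited to what the documents allow: 4% of the sample per affected patient at n = 25, 2% at n = 50. They give no rate of supplement use; Section 2.1 mentions only strong public acceptance. Nor do they give an effect of any such product on the markers, or the distribution of G. A reader might infer that the results are materially biased; that cannot be shown. The herbal case is the more plausible, since it needs only slightly more than a week between biopsy and first dose.

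The conclusion assumes that the initial biopsy in 7.3 is the diagnostic biopsy used as baseline, and that exclusion 4 is applied as written.

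**What to change.** 1. **Section 3.2, exclusion 4.** Anchor it to the biopsy for both classes, for example: *Any use of a ginseng product, or of a herbal or alternative product without FDA approval, between six weeks before the diagnostic biopsy and first dose.* This matches the look-back in 7.3 and the anchor of exclusions 3, 13 and 14. Shortening 7.3.3 to agree with exclusion 4 would make the text consistent but leave the herbal-exposed baseline in place.
2. **Section 10.** Cite 6.6, and add use of a 7.3 product during the study. State that use before enrollment is an eligibility matter only and not a ground for removal.
3. **Section 5.1.2 and the case report form.** Record the last date of any ginseng or herbal use, reaching back to six weeks before the biopsy.
4. **Section 16.0.** For patients already enrolled under the present exclusion 4, analyze everyone with paired tissue. Section 6.7 already implies this, since tissue is studied even when LEAG is stopped early. Then repeat the paired tests without known pre-biopsy users, and report how many have unknown history.

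**Cost.** Text edits, one screening question and one repeat of the paired tests. The re-anchored criterion looks back at a biopsy already taken, so a patient cannot meet it by waiting; some accrual will be lost, by a number the documents do not allow one to estimate. Version 1.8 (2018) revised the objectives according to available data, which suggests that dosing may be over. Items 1 to 3 would then have no effect on enrollment, but item 4 could still be done from chart history.

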11.0 ADVERSE EVENTS: LIST AND REPORTING REQUIREMENTS

11.1 Adverse Event Characteristics

- **CTCAE term (AE description) and grade:** The descriptions and grading scales found in the revised NCI Common Terminology Criteria for Adverse Events (CTCAE) version 3.0 will be utilized for AE reporting. All appropriate treatment areas should have access to a copy of the CTCAE version 3.0. A copy of the CTCAE version 3.0 can be downloaded from the CTEP web site (<http://ctep.cancer.gov>).
- **“Expectedness”:** AEs can be ‘Unexpected’ or ‘Expected’
- **Attribution** of the AE:
 - Definite – The AE *is clearly related* to the study treatment.
 - Probable – The AE *is likely related* to the study treatment.
 - Possible – The AE *may be related* to the study treatment.
 - Unlikely – The AE *is doubtfully related* to the study treatment.
 - Unrelated – The AE *is clearly NOT related* to the study treatment.

11.2 Adverse Event (AE) Reporting

An adverse event is any untoward medical occurrence in a patient that does not necessarily have

a causal relationship with the study intervention. An AE can, therefore, be any unfavorable and unintended sign (including an abnormal laboratory finding), symptom or disease temporarily associated with the use of a medical treatment or procedure (attribution of unrelated, unlikely, possible, probable, or definite).

Adverse events will be reported once treatment with the study agent begins to the Chairperson of the Springfield Committee for Research Involving Human Subjects (SCRIHS) at Southern Illinois University School of Medicine, [name], [contact].

Submission requirements of AE's, as defined by the SCRIHS procedure manual, will be strictly adhered to.

Adverse events that are expected and outlined in the pre-op discussion and/or listed in the surgical consent as related to surgery or anesthesia will not be reported.

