5.7 Study Role-Out: Additional Procedures for the First 5 Patients

Additional procedures will be conducted to evaluate the effects of LEAG on platelet function. The first 5 patients enrolled will have platelet function assessed prior to surgery with an interim analysis of platelet function and bleeding complications prior to additional patient enrollment to determine if platelet function should be evaluated in all study patients. After 5 patients have completed the study protocol a safety meeting will convene to determine if pre-operative assessment of platelet function is needed in all study patients. The following procedures have been added for the first five patients.

- 5.7.1 Added Exclusion Criteria
 - Role-out patients taking aspirin, other anti-coagulants, or anti-platelet aggregate are excluded at this time. Platelet Function Assay -100 may be affected by anti-coagulant use.

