5.7.3 Added post-LEAG but pre-surgical laboratory test

- Repeat Platelet Function Assay-100 test prior to surgery (2 citrate tubes of blood drawn day of surgery)

5.7.4 Interim Analysis of Platelet Function Assay completed following completion of 5 subjects. All PFA-100 results were within normal limits. Recommendations from Data Review Team state that further Platelet Function Assay testing is not necessary.

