6.4 Mechanism of Action

The major active components of ginseng are the ginsenosides found within the compound. Ginsenosides, also called panaxosides, are triterpenoid saponin glycosides. Asian ginseng contains up to 13 different ginsenosides which may have opposing actions on one another. Small animal tests have indicated that the active components of ginseng can prolong exercise time,

stimulate protein synthesis, inhibit platelet aggregation, stimulate the proliferation of hepatic ribosomes, prevent stress-induced ulcers, and increase the activity of interferons (clinical pharmacology). The antiplatelet effect appears to be a result of the activity of panaxynol and ginsenosides Ro, Rg1, and Rg2. Enhanced nitric oxide production in the lung, heart, and kidney, as well as the corpus cavernosum has been proposed as a mechanism of action. Various glycans have demonstrated a hypoglycemic effect in normal mice (clinical pharmacology). The ginsenosides found within the gelatin encapsulated lyophilized water-extract of American Ginseng root used in this study are as follows:

Ginsenosides per gram of Gelatin Encapsulated lyophilized water-extract of American Ginseng Root

Ginsenoside	mg
Rg1	2.38
Re	16.3
Rf	0
Rb1	25
Rc	4.60
Rb2	0.81
Rd	7.75
Total	40.04

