11.3 Safety Reporting Requirements for IND Holders

In accordance with 21 CFR 212.32, sponsor-investigators of studies conducted under an IND must comply with following safety reporting requirements:

1. Expedited IND Safety Reports:

- Seven Calendar-Day Telephone or Fax Report

The Sponsor-Investigator is required to notify the FDA of any fatal or life-threatening adverse event that is unexpected and assessed by the investigator to be possibly related to the use of LEAG. An unexpected adverse event is one that is not already described in the Investigator Brochure. Such reports are to be telephoned or faxed to the FDA within seven calendar days of first learning of the event. Each telephone call or fax transmission (see fax number below) should be directed to the FDA new drug review division in the Center for Drug Evaluation and Research or in the product review division for the Center for Biologics Evaluation and Research, whichever is responsible for the review of the IND.

- 15 Calendar-Day Written Report

The Sponsor-Investigator is also required to notify the FDA and all participating investigators, in a written IND Safety Report, of any serious, unexpected AE that is considered possibly related to the use of LEAG. An unexpected adverse event is one that is not already described in the Investigator Brochure.

Written IND Safety Reports should include an Analysis of Similar Events in accordance with regulation 21 CFR § 312.32. All safety reports previously filed with the IND concerning similar events should be analyzed. The new report should contain comments on the significance of the new event in light of the previous, similar reports.

Written IND safety reports with Analysis of Similar Events are to be submitted to the FDA and all participating investigators within 15 calendar days of first learning of the event. The FDA prefers these reports on a MedWatch 3500A Form but alternative formats are acceptable (e.g. summary letter).

FDA fax number for IND Safety Reports:

[name] ([name])

MedWatch 3500A Reporting Guidelines

In addition to completing appropriate patient demographic and suspect medication information, the report should include the following information within the Event Description (Section 5) of the MedWatch 3500A form:

- Treatment regimen (dosing frequency, combination therapy, administration dates);
- Protocol description (and number, if assigned);
- Description of event, severity, treatment, and outcome, if known;

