With respect to the safety goals of this study, toxicities specific to this therapy are not known at this time. Therefore, patients will be monitored for unexpected toxicities and if any serious side effects are observed, an independent monitoring committee will examine the data and evaluate the appropriate course of the study. At the conclusion of the study, all unexpected toxicities will be summarized and reported.

To evaluate a potential effect of LEAG on platelet function, a Platelet Function Assay-100 test will be conducted on the first five patients enrolled. Platelet function will be assessed prior to LEAG administration and prior to surgery on the day of surgery. All adverse events will be

monitored for 30 days beyond the last dose of LEAG, including bleeding complications. Following completion of the study protocol by 5 patients the Data Safety Monitoring Committee will review the adverse events associated with LEAG administration paying particular attention to platelet function. The committee will make a recommendation on continued monitoring of platelet function or its removal from required study procedures for the remainder of patients enrolled. – See section 5.7.4

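### The surgical-event exemption in section 11.2 has no exception for events possibly related to LEAG, so some bleeding could be collected but neither reported nor summarised

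*Combined protocol and SAP*

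**What the plan says.** The reporting rule is in section 11.2. It says that events which are expected and were raised with the patient before the operation, and/or those "listed in the surgical consent as related to surgery or anesthesia will not be reported". The section names the local IRB as the recipient and defers to that board's procedure manual for submission requirements. The sentence has no exception by attribution, grade or seriousness.

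Elsewhere the protocol treats bleeding as something to watch:

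- Section 6.4, drawing on small animal tests, reports inhibition of platelet aggregation: "The antiplatelet effect appears to be a result of the activity of panaxynol and ginsenosides Ro, Rg1, and Rg2". Of those four, only Rg1 appears in the LEAG content table, at 2.38 mg per gram, which is the daily dose.
- Section 5.7 plans, for the first five patients, an "interim analysis of platelet function and bleeding complications prior to additional patient enrollment".
- Section 14.7 (Analysis of Safety) has adverse events "monitored for 30 days beyond the last dose of LEAG, including bleeding complications".

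Other sections limit what the exemption can do:

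- Section 5.5 has the adverse event log completed on the day of surgery.
- Section 5.6 collects events through the post-surgery visit, and related or possibly related ones for at least 30 days after the last dose.
- Section 11.1 requires CTCAE grade and attribution.
- Section 11.3 sends serious, unexpected, possibly related events to the FDA, with its own test: "An unexpected adverse event is one that is not already described in the Investigator Brochure".
- Section 14.2 has serious and unexpected reactions notified promptly to the IRB, also by reference to the Brochure.
- Section 14.7 promises an end-of-study summary of unexpected toxicities. It names no other.

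**The concern.** Every patient has surgery the day after her last dose. If LEAG affected bleeding, the effect would most likely show during or soon after the operation, when a bleed is also an ordinary surgical complication. Section 11.2 sorts such an event by whether it was foreseen as a surgical risk, and does not ask whether LEAG may have contributed. One event can be both, and the rule is silent on that overlap.

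The word expected adds to the difficulty. Section 11.1 uses it without a definition, 11.2 ties it to the pre-operative discussion and surgical consent, and 11.3 and 14.2 tie it to the Investigator Brochure. Section 14.7 limits the final summary to unexpected toxicities without saying which test applies. In a single-arm study of 25 to 50 patients, a complete count of bleeding events with attribution is the main safety evidence on this question, and no rule requires it to be presented.

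**Working it through.** The plan states no figure on this point, so the check is mainly a reading of the rules together, with two short calculations for context.

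**1. Which route catches which bleed.** Take a peri- or post-operative bleed judged possibly related to LEAG, and assume that the surgical consent lists bleeding. Neither the consent nor the Brochure is in the documents, so all four cases are shown.

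| Bleed | 11.2 (IRB) | 11.3 (FDA, expedited) | 14.2 (IRB, prompt) | 14.7 final summary |
|---|---|---|---|---|
| Serious, not in Brochure | Exempt | Yes | Yes | Depends on the test of expected |
| Serious, in Brochure | Exempt | No | No | No |
| Non-serious, not in Brochure | Exempt | No | No | Depends on the test of expected |
| Non-serious, in Brochure | Exempt | No | No | No |

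In the two rows marked as depending, the bleed is in the final summary if unexpected means absent from the Brochure, and out of it if the surgical sense of 11.2 carries over. Only the first row has a firm reporting duty, and there 11.2 points the other way from 11.3 and 14.2. In the other three rows the event is collected but no explicit rule sends it to the IRB or triggers an expedited FDA report.

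Two softer provisions remain. Section 14.2 asks for the IRB to be kept informed of significant adverse events, a term it does not define. Section 14.7 has an independent committee look at the data if serious side effects are observed, which does not help the non-serious rows.

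**2. When the exemption can apply.** Inputs: 5 to 14 treatment days and a last dose the day before surgery (5.3), and 30 days of follow-up for related or possibly related events after the last dose (5.6). All 30 follow-up days fall on or after the day of surgery.

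- Shortest treatment: 30 / (5 + 30) = 30/35 = 86%.
- Longest treatment: 30 / (14 + 30) = 30/44 = 68%.

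This is a share of calendar time. The exemption depends on the type of event, so the figure does not say what share of events would be lost.

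**3. What the five-patient check shows.** Section 5.7.4 records that "All PFA-100 results were within normal limits" and that further assay testing was judged unnecessary. It gives no bleeding outcome. Suppose, as an assumption, that none of the five bled. The one-sided 95% upper bound on the true rate is 1 − 0.05^(1/5) = 45%. The chance of seeing at least one event in five, 1 − (1 − p)^5, for assumed true rates p is:

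| p | 2% | 5% | 10% | 20% |
|---|---|---|---|---|
| Chance of at least one in 5 | 10% | 23% | 41% | 67% |

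The five also differed from later patients: 5.7.1 and 7.3.4 restrict aspirin and other anticoagulants in the first five only. The remaining 25 − 5 = 20 to 50 − 5 = 45 patients have no scheduled review of bleeding.

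**The case against.** The strongest reply is that 11.2 is about submissions to the IRB and not about data collection. That is right. Nothing in 11.2 removes an event from the log, and 5.5, 5.6, 11.1 and 14.7 keep recording, grading, attribution and 30-day monitoring in force. A reader might infer that bleeding disappears from the trial's data, or that a finding of safety would be produced by the reporting rule alone. The documents do not support either reading.

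A second reply is that the worst case is covered: a serious, possibly related bleed absent from the Brochure goes to the FDA under 11.3 and to the IRB under 14.2. This also stands. The conflict there is one of wording, and an investigator following all the sections would report the event.

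Third, the wording of 11.2 is narrower than a quick reading suggests. It speaks of events that are expected and of events listed as related to surgery or anesthesia, and its and/or can be read as requiring an event to be expected as well as listed. The IRB's procedure manual may also restore some reports, but it is not in the documents.

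Fourth, the protocol does not state that LEAG causes surgical bleeding. Section 6.4 describes an antiplatelet mechanism from animal work on ginseng in general, 7.1 does not list surgical bleeding among side effects, patients at high risk of bleeding or on coumadin are excluded, and the platelet assays were normal. So this is a precautionary concern. It is nevertheless the protocol's own concern, and five normal assays are weak grounds for closing it.

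Finally, the objectives are biomarker objectives and there is no control arm, so IRB reports alone would not separate LEAG from surgery. That lowers the severity. It does not explain why events that are monitored should be left out of the summary.

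**Conclusion.** The concern holds in a limited form. Section 11.2 lacks an exception for surgical complications possibly related to LEAG. As a result, a possibly related bleed that is non-serious, or already in the Brochure, has no explicit route to the IRB or to an expedited FDA report. If it is classed as expected, it is also outside the only end-of-study safety summary that the plan promises. This is inconsistent with the emphasis on bleeding in 5.7 and 14.7.

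The conclusion rests on two assumptions: that the surgical consent or pre-operative discussion lists bleeding, and that 11.2 is applied as written. The number of events affected cannot be estimated from the documents. A reader might take 68% to 86% as the proportion of events lost; it is only the part of the related-event window in which the exemption could operate. Severity is moderate: a real gap in safety reporting that leaves data collection and the primary analysis untouched.

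**What to change.** Four wording changes would reconcile the sections:

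1. In 11.2, limit the exemption to events assessed as unrelated or unlikely related to LEAG.
2. State in 11.2 that the exemption does not override 11.3, 14.2 or the bleeding monitoring in 14.7.
3. Judge expectedness for LEAG by the Investigator Brochure throughout, including in 11.1 and 14.7.
4. Extend the end-of-study summary in 14.7 to all bleeding events, with CTCAE grade and attribution.

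The cost is a short amendment, a few more IRB reports and one extra table for 25 to 50 patients. Grade and attribution are already collected, so no new data are needed. The downside is that some routine surgical bleeding will be counted and, without a control arm, cannot be separated from any effect of LEAG; the table should say so. The documents do not state whether accrual has closed. If it has, the fourth change can still be made from events already collected.
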